3.1 Local sample size

We expect to enroll 90 participants at SRALab: 6 occupational or physical therapists plus 84 of their patients with SCI (of which $n = 18$ patients will only be enrolled as audio-only test participants).

The recruitment breakdown and timeline is as follows:

- Recruitment phase 1: 6 occupational or physical therapists
- Recruitment phase 2: 12 patients with SCI, 2 patients per therapist, will be recruited as audio-only test participants to assess baseline motivational interviewing skills prior to therapist randomization and training.
- Recruitment phase 3: Half ($n = 3$) of the therapists at each site will be trained in MI, so we will recruit 6 additional patients (2 per MI-trained therapist) as audio-only test participants to assess MI competency during the initial MI training phase.
- Recruitment phase 4: We will recruit 60-66 patients with SCI—10-11 patients per enrolled therapist—for the experimental phase, which includes audio recording of therapy sessions plus two additional questionnaires.

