3.2 Total sample size

Across sites, we expect to enroll 180 participants: 12 OT/PT's (6 per site) and 168 patients with SCI (84 per site).

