3.3 Sample size justification

We anticipate a sufficient number of patients; full time therapists are budgeted to work with six patients daily while half time therapists are budgeted to work with three patients daily.

The effect size obtained from the pilot study was 0.56 (Cohen's *d*). Based on the G*Power 3.1.9.6 program we would need to study 104 patients (52 per group) to adequately power the study assuming an alpha level of .05, power = .80, two-tailed test, and 1:1 allocation. We anticipate 20% attrition rate leading to a total of 126 patient participants.

4.0 Recruitment and Screening Methods:

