- Once the research team enrolls 6 physical therapists or occupational therapists, demographic information will be collected by the research assistant via REDCap survey (see 'DemographicSurvey' under 'supporting documents'). The therapist participant may fill out the demographic survey via REDCap themselves if they prefer – the research assistant will review the answers and follow up with participants in-person to clarify as needed..
- All therapists will audio record two therapy sessions with SCI/D patients wearing a digital recorder on their name badge lanyard or on their clothing. This will provide a baseline level of MI skills. Audio-only test patients will sign an authorization to have their therapy session recorded (see "EditedSRAlabAudioConsentForm"). We will not obtain full informed consent from the audio-only patients because their identities will not be recorded and they will not participate in the patient questionnaires described below. The test audio recordings obtained in steps 8.1 and 8.2 will be destroyed after therapists' motivational interviewing skills are assessed.
- After all baseline recordings are complete, the data manager will perform a central computer-generated randomization and then transmit treatment allocation to [name], the MI trainer, via secure email. [name] will then contact enrolled PTs and OTs at each site to set up training as indicated. Randomization will be stratified based on therapist type (PT vs.

OT). The allocation sequence will be concealed from any study staff involved in enrollment of participants or data collection via a restricted access database program.

- Half of the therapists will be assigned to the experimental Motivational Interviewing group, and the other half will be assigned to the control group.

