8.3 Recruit participants – Inpatients with SCI

- Once the MI trained PTs and OTs achieve basic MI competency, the experimental phase of the study will begin. The research assistants at both sites will approach a convenience sample of eligible inpatients that the PTs and OTs in the study are treating, for participation in the study. The research assistants will recruit and consent 10-11 inpatients for each of the therapists who were trained in MI as well as for each of the therapists who were not trained in MI for a total of 126 inpatients.

- The research assistants will ask the therapists when they feel comfortable to add another patient participant to their research caseload so as not to overburden the therapist with the research tasks. The patients will be kept blinded to whether their therapist has been trained in MI or not.

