10.1 Randomization and blinding

Half of the therapists will be trained in motivational interviewing, and the other half will proceed with normal care. As such, therapist participants cannot be blinded to their group assignment. Therapists who are not assigned to the MI group will have the opportunity to complete the training after completion of the study intervention.

Group assignments will be randomized by the study investigator, but the rest of the research team participating in data collection will be blinded to MI assignments. The research assistants collecting data and observing therapy sessions will not be trained in MI to further prevent bias.

Patient participants will be blinded to their group assignment—the therapists will be instructed not to disclose whether they are using MI techniques during therapy sessions or not. Patient participants will be told the nature of the intervention during the informed consent process.

11.0 Consent Process:

- 11.1** Written, informed consent will be obtained for all participants in the study, including therapist participants (n = 6 local) and SCI participants (n = 66 local).
- 11.2** The informed consent process will take place at Shirely Ryan AbilityLab by IRB-approved team members.
- 11.3** The research member obtaining consent will explain the study to potential participants in-person and provide a hard copy of the consent document for review. Participants will be encouraged to read the full consent document and ask any questions prior to signing. Two copies of the consent form will be created for each enrolled participant—the original copy will be stored in locked filing cabinets on the study team unit, and the second copy will be provided to the participant for their personal records. Consent may also be obtained online via REDCap if the participant prefers this process to a hard copy.
- 11.4** Any potential patient participant may refuse to participate and this will not impact the care that they receive at SRALab. Similarly, therapists' participation in this research study is entirely voluntary and unrelated to their responsibilities as an employee of SRALab. They will be neither rewarded nor penalized for their activities related to the research study. Also, these activities should not impact their responsibility to perform their duties as an SRALab-employed therapist. Participants can also withdraw at any time by verbally stating that they do not wish to participate anymore.

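### The enrolment total of 126 in sections 3.3 and 8.3 does not cover the protocol's own 20% attrition: keeping 104 patients needs 130 (minor correction)

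*Protocol*

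**What the plan says.** Protocol section 3.3 takes d = 0.56 from the pilot, a two-sided alpha of 0.05, power of 0.80 and 1:1 allocation, and concludes that "we would need to study 104 patients (52 per group) to adequately power the study". It then adds the allowance for loss: "We anticipate 20% attrition rate leading to a total of 126 patient participants". Section 8.3 carries the same total into the recruitment instruction, at 10 to 11 inpatients per trained therapist and likewise "for each of the therapists who were not trained in MI for a total of 126 inpatients".

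The other enrolment figures are these:

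- Section 3.1, phase 4, gives a range for one site: "We will recruit 60-66 patients with SCI—10-11 patients per enrolled therapist—for the experimental phase".
- Section 3.1 also gives a fixed local total: "84 of their patients with SCI (of which $n = 18$ patients will only be enrolled as audio-only test participants".
- Section 3.2 gives the total over both sites: "168 patients with SCI (84 per site".
- Section 11.1 gives the local numbers to be consented: "therapist participants (n = 6 local) and SCI participants (n = 66 local".

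**The concern.** Section 3.3 states a number of patients needed, a loss rate and an enrolment total, and the three do not fit together. An attrition rate is the share of enrolled patients who are lost, so the number needed has to be divided by the share that remains. The total of 126 is smaller than that division gives.

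The stated target would therefore miss the protocol's own requirement if attrition ran exactly as expected. Recruitment under 8.3 could also close at 126, although the totals elsewhere in the protocol would allow a few more patients. The lower end of the range in 3.1 falls further short.

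**Working it through.** **Inputs.** From 3.3: d = 0.56, two-sided alpha 0.05, power 0.80, 1:1 allocation, 104 patients needed, 20% attrition, 126 enrolled. From 3.1, 3.2 and 11.1: 60 to 66 trial patients per site, 84 local patients of whom 18 are audio-only, 168 patients over two sites, 66 local patients consented.

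**1. The plan's base figure.** For a two-sample t-test with n per group, power comes from the noncentral t distribution with 2n − 2 degrees of freedom and noncentrality d × √(n/2). Solving for 80% power at d = 0.56 gives n = 51.03, rounded up to 52 per group, or 104. Power is 79.97% at 51 per group and 80.74% at 52. The figure of 104 is reproduced.

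**2. The inflation for attrition.**

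- Needed: 104 / (1 − 0.20) = 130, or 52 / 0.80 = 65 per group.
- Left from 126 at 20% loss: 126 × 0.80 = 100.8, which is below 104.
- Losses that 126 can absorb: 126 − 104 = 22, and 22/126 = 17.5%. Expected losses at 20% are 25.2.

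**3. Where 126 may come from.** The protocol does not show the step. Multiplying by 1.20 and rounding up within each group gives it: 52 × 1.20 = 62.4, hence 63, and 2 × 63 = 126. So does 12 therapists × 10.5 patients. Either is an inference.

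**4. The other totals.**

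- 3.1 range: 2 × 60 = 120 to 2 × 66 = 132.
- 3.1 fixed total: 84 − 18 = 66 per site.
- 3.2: 168 − 2 × 18 = 132.
- 11.1: 66 local, hence 2 × 66 = 132 if the second site matches, as 3.2 implies.

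**5. Consequences at d = 0.56 and 20% loss.** Power uses the test in step 1, with the remaining patients split equally and not rounded to whole numbers.

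| Enrolled | Left after 20% loss | Power | Losses before falling below 104 |
|---|---|---|---|
| 120 (lower end of 3.1) | 96.0 | 77.5% | 16 (13.3%) |
| 126 (3.3 and 8.3) | 100.8 | 79.5% | 22 (17.5%) |
| 130 (104/0.80) | 104.0 | 80.7% | 26 (20.0%) |
| 132 (fixed totals) | 105.6 | 81.3% | 28 (21.2%) |

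**The case against.** The strongest reply is that nothing of substance turns on this. The target is 80% power, and 126 enrolled gives 79.5% after 20% loss, half a point short. Part of the gap between 79.5% and 80.7% is only the surplus from rounding 51.03 up to 52 per group. That stands, and it settles the weight of the point. It does not make the sentence in 3.3 correct: the requirement stated there is 104 patients, and 126 does not deliver 104 at the rate stated beside it.

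A second reply is that 20% was meant as over-recruitment relative to 104, not as loss from those enrolled. That would explain 126, but the text calls it attrition, and the attrition that 126 covers is then 17.5%. Section 3.3 would still need rewording.

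A reader might also infer that the protocol sets two contradictory totals, 126 and 132. The documents do not support that strong a reading. The range in 3.1 runs from 120 to 132 overall and contains 126; 8.3 gives 126 in the same sentence as 10 to 11 per therapist; and 84, 168 and 66 can be read as the upper limit of enrolment. What remains is that 126 is not labelled as a target, nor 132 as a maximum.

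**Conclusion.** The point holds as a minor correction. At 20% attrition the total of 126 leaves about 101 patients, three short of the 104 that 3.3 requires, and enrolment would have to be 130, four more than stated. The shortfall in power is about 0.5 points below the planned 80%. At the lower end of 3.1 it is 2.5 points (77.5%).

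This rests on three things: attrition read as a share of those enrolled, losses spread equally over the groups, and the protocol's d = 0.56 and individual-level test taken as given.

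A reader might go on to infer that the trial is materially underpowered, either because therapists and not patients are randomized or because the pilot means and SDs do not obviously yield 0.56. Neither follows here. The protocol gives no intraclass correlation from which to size a clustering effect, and that is a separate question from the inflation step. It reports the pilot result from a multi-level model adjusted for sex, age and trauma type and does not say which SD underlies d, so a mismatch is not shown. Nor does the correction require exactly 11 patients from every therapist.

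**What to change.** In 3.3 and 8.3, replace 126 with a minimum of 130 patients (104/0.80; 65 per group), and state 132 (66 per site) as the planned maximum, in line with 3.1, 3.2 and 11.1. In 3.1, phase 4, raise the lower end of the range from 60 to 65 per site. The 10 to 11 patients per therapist can stay, provided that no more than two of the 12 therapists stop at 10: 10 × 11 + 2 × 10 = 130. For 65 per group and per site, those two would be in different groups and at different sites.

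Alternatively, keep 126 and correct the sentence around it: give the attrition it allows as 17.5%, or the power after 20% loss as 79.5%. In that case the lower end in 3.1 should still rise, to 63 per site (126/2), because 120 falls short of 126.

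The cost is a text change in three sections. The totals in 3.1, 3.2 and 11.1 do not change. Measured against 126, the first option means at least four more patients, with up to $50 each in patient payments (4 × $50 = $200) plus their weekly participation ratings, recordings and MI coding. The alternative adds no patients to the 126.

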4.1 Recruitment and screening of therapists

The research team at SRALab will recruit 6 rehabilitation therapists—ideally 3 physical therapists and 3 occupational therapists—working on the designated inpatient SCI units (floor 21 and 22). Therapists will be approached on the therapy floor during breaks in their workday using the therapist recruitment script and therapist recruitment flyer. The research team will notify and work with the allied health managers on each floor as needed to coordinate recruitment efforts with therapist schedules.

The research assistant will screen interested therapists based on the inclusion criteria: (1) inpatient spinal cord injury rehabilitation therapist working on floors 21 or 22 for at least 3 months, (2) willing and able to participate in 16 hours of MI training, and (3) willing to record audio of therapy sessions with enrolled patients.

Therapists who meet eligibility criteria will proceed with informed consent if still interested after screening questions. The research assistant will obtain written informed consent either on paper or REDCap e-signature. The therapist will be given a copy of the consent form, and they will be encouraged to read through the consent form and ask questions prior to enrolling.

4.2 Authorization form for audio-only test patients

As described in the sample size breakdown, 18 patients with SCI will be audio recorded to (1) assess baseline motivational interviewing skills (n = 12, 2 patients per therapist) and (2) assess post-training motivational interviewing skills (n = 6, 2 patients per MI-trained therapist). This activity does not qualify as human

subjects research because the patient identities will not be documented by the research team or associated with the recordings, and no survey data will be obtained. The audio will only be used to assess MI skills of the therapist participants. The recordings will be destroyed once the pre-experimental phase of the study is completed. Please see “SRAlabAudioConsentForm” in lieu of full informed consent document.

4.3 Recruitment and screening of inpatients with SCI

A convenience sample of patients with SCI will be recruited based on new admissions to inpatient rehabilitation and the participation of their rehabilitation therapist in the study. The research team will approach patients assigned to one of the enrolled therapists at the time of their admission to an SRAlab inpatient SCI unit (on floor 21 or 22).

A research assistant will screen patients newly admitted to the 21 or 22 floor for presence of a traumatic or non-traumatic SCI via admission records in Cerner. Patients must be 18 years or older at time of admission and must speak English without a translator. Potential participants must also agree to having audio recordings of their therapy sessions.

The research team will communicate with the enrolled therapist to schedule a time before, during, or after rehabilitation sessions to recruit and screen patients. We will approach eligible patients using the recruitment script and flyer after assessing initial eligibility through medical records.

Interested patients will review the informed consent document with a member of the research team.

During the consent process, patients must agree to audio recordings of their therapy sessions—they will be informed that the audio recordings focus on the therapist and not the patient, but both sides of the conversation are needed to provide context to the therapist’s verbiage. We will instruct therapists to avoid using patients’ full names when recording therapy sessions. Audio recordings will be uploaded to Shirley Ryan AbilityLab OneDrive with limited permissions to maintain privacy of therapists and patients.

5.0 Research Locations:

This protocol describes research activities that will take place at Shirley Ryan AbilityLab under review of the Northwestern IRB. Therapy sessions will be held and recorded in the usual SCI rehabilitation units on the 21 or 22 floor. Research documents will be saved on the secure SRAlab network using SRAlab-approved devices. The research team will use REDCap to collect survey data and otherwise store participant information in password-protected files on the SRAlab server.

An identical protocol will be conducted at Baylor Scott White in Texas which will be reviewed under their local IRB. Any information that the SRAlab research team must share with the Baylor research team will be stripped of direct patient identifiers, such as full name and address.

6.0 Multi-Site or Collaborative Research:

6.1 Primary research sites

This study is funded by the Craig H Neilsen Foundation (non-federal) and involves two primary research sites, SRALab (Chicago, IL) and Baylor Scott White (Dallas, TX).

The Principal Investigator at SRALab is [name], PhD, RN, Associate Director of the Center for Rehabilitation Outcomes Research. The Co-Investigator at Baylor Research Institute is [name], Research Center Director.

Each site will administer an identical protocol under the review of their local IRB.

6.2 Motivational Interviewing Consultant

[name] is a clinical psychologist and Professor in the Department of Rehabilitation Medicine at the University of Washington. [name] is a co-Investigator on this study, serving as an expert on motivational interviewing (MI).

He is a member of the international Motivational Interviewing Network of Trainers (MINT). He collaborated with [name] on the pilot study that set the stage for this trial. As a Co-Investigator, he will assist with training and coaching of the PTs and OTs to use motivational interviewing techniques in their work with inpatients with SCI. He will also assist with interpretation of study results, co-authoring publications and presentations, and contributing to other dissemination efforts.

The University of Washington is not a research site, and [name] will not be involved in the recruitment or data collection activities taking place at SRALab and Baylor. He will assist the Principal Investigator in motivational interviewer training, initial assessment of therapist MI competency, and analysis, interpretation, and dissemination of findings. These activities will take place through secure, remote technology platforms hosted by the primary research sites, SRALab and Baylor.

7.0 International Research (where data collection will occur outside the United States and U.S. territories, including online activities)

N/A

8.0 Procedures Involved:

Please check the boxes for all applicable data collection procedures you plan to use:

- One-on-one interviews
- Focus Groups
- Questionnaires/surveys
- Secondary Data Analysis (medical record data, educational records, government or private sector datasets, etc.)
- Ethnographic observation
- Physiological measurements (e.g., EEG, EKG, MRI)
- Biospecimen collection (saliva samples, blood draws, hair samples, etc.)
- Mobile applications/data collection devices (e.g., Fitbits, actigraphs, etc.)
- Behavioral decision making tasks (e.g., puzzles, interactive games, etc.)
- Physical activities such as walking and other forms of exercise
- Other procedures (briefly list types of procedures here if not covered by the check-boxes above): _____

8.1 Baseline data collection and randomization of therapists:

- Once the research team enrolls 6 physical therapists or occupational therapists, demographic information will be collected by the research assistant via REDCap survey (see 'DemographicSurvey' under 'supporting documents'). The therapist participant may fill out the demographic survey via REDCap themselves if they prefer – the research assistant will review the answers and follow up with participants in-person to clarify as needed..
- All therapists will audio record two therapy sessions with SCI/D patients wearing a digital recorder on their name badge lanyard or on their clothing. This will provide a baseline level of MI skills. Audio-only test patients will sign an authorization to have their therapy session recorded (see "EditedSRAlabAudioConsentForm"). We will not obtain full informed consent from the audio-only patients because their identities will not be recorded and they will not participate in the patient questionnaires described below. The test audio recordings obtained in steps 8.1 and 8.2 will be destroyed after therapists' motivational interviewing skills are assessed.
- After all baseline recordings are complete, the data manager will perform a central computer-generated randomization and then transmit treatment allocation to [name], the MI trainer, via secure email. [name] will then contact enrolled PTs and OTs at each site to set up training as indicated. Randomization will be stratified based on therapist type (PT vs.

OT). The allocation sequence will be concealed from any study staff involved in enrollment of participants or data collection via a restricted access database program.

- Half of the therapists will be assigned to the experimental Motivational Interviewing group, and the other half will be assigned to the control group.

8.2 Train therapists in Motivational Interviewing

- MI training will follow the standard, evidence-based training model recommended within the MI expert community of 16 hours of training.(Miller, Yahne et al, 2004 Journal of consulting and clinical psychology, 72: 1050-1062.) [name] is an experienced trainer and a member of the international MI Network of Trainers (MINT). [name] (co-I, University of Washington) is also an experienced trainer and member of the MINT will assist her with the training. The training will take place virtually via Zoom in eight 2-hour time blocks either weekly or bi-weekly dependent on the therapists' work schedule. Training times will take place outside of patient treatment times.
- After all training is complete, each therapist in the MI training and coaching group will provide [name] with two audio recordings so that she can assess the therapists for MI competency using the MITI 4.2.1. Based on prior research training of rehabilitation professionals as well as published research, basic competency in MI can be attained with this amount of training and coaching. (Miller, Yahne, et al., 2004).
- We will ask the therapists who are trained in MI not to share any of the training with the untrained therapists over the course of the study. We will provide free MI training to the untrained therapists once the treatment phase of the study is complete.
- Therapist participants in the MI group will receive \$200 as compensation for participation in training. Those in the control group will be offered the MI training and \$200 compensation at the end of the study. All payment will be administered via ClinCard.

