- A research assistant will administer the Spinal Cord Injury Functional Independence (SCI-FI) via interview within approximately one week of patient discharge from inpatient rehabilitation. A research assistant will administer the Participation Assessment with Recombined Tools-Objective (PART-O) to patient participants at 6 months post-discharge from inpatient rehabilitation. Scores will be recorded on a fillable PDF and then entered into REDCap.

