8.5 Study Duration and Compensation

- Enrolled therapists are expected to be in the study for the duration of the data collection window, approximately 1 year.
- Therapists will be compensated \$200 via ClinCard for participating in MI training and \$5 for uploading each audio recording of their therapy session with enrolled patients. We expect therapist participants to upload 2 recordings per week per patient participant.
- Patient participants will receive \$25 for completion of the SCI-FI measure and \$25 for completion of the PART-O measure.
- All research payment will be administered via ClinCard

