15.0 Audio/Video Recording/Photography

Therapy sessions will be audio recorded 2 times per week on mobile audio recording devices. The research team led by [name] will provide the therapist participants with the devices after they are enrolled in the study. The recordings will be the length of the therapist's typical session, approximately one hour but up to two hours. The therapists will download the audio recordings to a secure file (Shirley Ryan AbilityLabMicrosoft Teams secure network). Then [name] and [name] will listen to a sample of the audio recordings and rate the therapists' competency in MI using the Motivational Interviewing Treatment Integrity skill coding system during the baseline and MI competency phase.

Audio recordings will be stored separately from participant identifiers and will be labeled with Subject ID #'s rather than names. Audio recordings will be uploaded to Shirley Ryan AbilityLab OneDrive with limited permissions to maintain privacy of therapists and patients.

Participants will be informed of audio recordings during the informed consent process and throughout their study participation period. Audio recordings will be deleted after completion of the data analysis period.

During the randomized control trial phase, one random recording per week per patient participant will be shared with the Motivational Interviewing Treatment Integrity coding lab who will rate the motivational interviewing skills of the therapists by listening to 20 minutes of the recording and rating the session using the MITI 4.2.1 rating scale. These scores will be used to provide feedback to the therapists on their MI skills and to guide coaching sessions of the therapists for their MI skills. Coaching sessions of the therapists will take place individually approximately monthly or more often as needed based on the MITI scores.

16.0 Potential Benefits of this Research:

16.1 Therapist participants will be trained in motivational interviewing, an evidence-based skill that requires at least 16 hours of training by a designated instructor. Therapists who are not randomly assigned to the MI group during the

study period will have the opportunity to be trained in MI after completion of the study period. CEU credits will be offered upon completion of the MI workshop.

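### The protocol gives conflicting times for training the control therapists, and the earlier one would put that training before many of the blinded 6-month PART-O interviews

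*Protocol*

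**What the plan says.** Four statements in the protocol time the training of control therapists.

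- Section 8.2, third bullet: "We will provide free MI training to the untrained therapists once the treatment phase of the study is complete".
- Section 8.2, fourth bullet: "Those in the control group will be offered the MI training and" $200 "compensation at the end of the study".
- Section 10.1: "Therapists who are not assigned to the MI group will have the opportunity to complete the training after completion of the study intervention".
- Section 16.1: therapists not randomised to MI during the "study period will have the opportunity to be trained in MI after completion of the study period".

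Section 8.4 has a research assistant administer the PART-O "to patient participants at 6 months post-discharge from inpatient rehabilitation". It is the 6-month measure that serves the community-integration part of Aim 2. Section 10.1 states that "the rest of the research team participating in data collection will be blinded to MI assignments" and gives no date at which that blind may end. On duration, Section 8.5 says only: "Enrolled therapists are expected to be in the study for the duration of the data collection window, approximately 1 year". It does not say whether that year includes the initial MI training or the 6-month follow-up.

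**The concern.** The end of treatment and the end of the study are different dates here, because the last PART-O falls at least 6 months after the last discharge. If control training follows the earlier timing, only control therapists attend a course while the interviewers' blind still has to hold.

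Section 3.1 gives six therapists per site, three per arm, so learning who the three controls are reveals the whole site's allocation. Research assistants recruit patients through their therapists (4.3, 8.3), so they can link each patient to a therapist. Therapists are told not to disclose MI use to patients (10.1), and trained therapists are told not to share the training with untrained ones (8.2). Nothing tells therapists to keep their training status from research assistants, and nothing separates the PART-O interviewers from therapist training.

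At stake is the stated blind for an interviewer-administered outcome, where knowledge of the arm could affect probing or scoring. PRPS ratings would be complete by then. SCI-FI is touched only for patients discharged after the treatment phase ends.

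**Working it through.** The protocol gives no figure for interviews outstanding when treatment ends, so there is none to reproduce. What follows is an estimate under stated assumptions.

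**1. The timings compared.** The third bullet of 8.2 and Section 10.1 point to the end of treatment, and both concern training only. The fourth bullet of 8.2 and Section 16.1 point to the end of the study or study period. Only the fourth bullet of 8.2 dates the control $200, and it uses the later time.

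**2. Inputs from the protocol.**
- 126 experimental-phase patients (8.3).
- 4 weeks of participation per patient (8.4): w = 4/4.345 = 0.92 months.
- PART-O 6 months after discharge (8.4).
- A data collection window of about 1 year (8.5).
- A course of eight 2-hour blocks, weekly or every second week (8.2), so about 8 to 16 weeks: d = 1.84 to 3.68 months.

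**3. Assumptions.** Accrual is even. The treatment phase runs T months, from first enrolment to the end of the last patient's 4 weeks. Discharge comes L months after enrolment, with L from 0.92 to 3. The protocol fixes neither T nor L.

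**4. Formula.** Patients enrol evenly from 0 to T − w. A patient enrolled at time e is due for PART-O at e + L + 6, which is outstanding at T if e > T − L − 6. Hence

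share outstanding = (6 + L − w) / (T − w).

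**5. Results.** For T = 12: L = 0.92 gives 6.00/11.08 = 54%, and L = 3 gives 8.08/11.08 = 73%. The table places 126 patients at even spacing, which differs from the formula by less than one percentage point.

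| T (months) | L = 0.92 | L = 3 |
|---|---|---|
| 12 | 54% (68 of 126) | 73% (92 of 126) |
| 15 | 43% (54) | 57% (72) |
| 18 | 35% (44) | 48% (60) |
| 24 | 26% (33) | 35% (44) |

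If the 1-year window also contains 2 to 4 months of initial MI training (T = 10 or 8, L = 0.92 to 2), the share is 66% to 99%. If the year must also contain the last PART-O, treatment ends by about month 6 and the share is 100%.

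**6. If disclosure comes only at the end of the control course.** Subtract d from the numerator: (6 + L − w − d) / (T − w). With T = 12 and L = 0.92 to 2, on the same 126-patient spacing, 37% to 48% are outstanding after an 8-week course and 21% to 31% after a 16-week course.

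**7. After the fix.** If control training waits for the last PART-O, 0 of 126 interviews are outstanding when it starts. That interview falls 6 + L − w months after treatment ends: 6.0 months at L = 0.92 and 8.1 months at L = 3.

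**The case against.** A reader might infer that control therapists are to be both trained and paid immediately when treatment ends. The text does not support that. The only sentence dating the control $200 puts it at the end of the study. Sections 8.5 and 14.0 tie the $200 to taking part in training, so early payment might follow early training, but that is inference. The third bullet of 8.2 and Section 10.1 can also be read as giving the earliest permissible point, in which case training at the end of the study satisfies all four statements. That reading is available, but the protocol does not state it.

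A reader might also infer that the interviewers will be unblinded. No section says so. Training is by Zoom outside treatment times (8.2), the MI trainer contacts the therapists, and allocation is held in a restricted database (8.1). The research assistants' documented contact with therapists belongs to recruitment and weekly observation, and the remaining PART-O interviews are with patients already discharged. This stands: unblinding is a possibility only.

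The added risk is also limited. The MI arm's own course, its $200, and the two extra test patients recruited for each MI-trained therapist (3.1) all come before the experimental phase. They could reveal the arms before any outcome is collected, and delaying control training does nothing about that. It is a reason for modest weight, not for leaving a second, avoidable exposure in place.

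Finally, the share outstanding is not the share interviewed by someone who knows the arm, and it rests on a treatment-phase length the protocol does not state. Both points stand.

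**Conclusion.** The conflict in timing is on the page and should be resolved. Under the earlier timing, control-only training can begin while many blinded PART-O interviews are due: about 54% to 73% for a 12-month treatment phase with even accrual and discharge 0.9 to 3 months after enrolment. The share is lower if the phase runs longer (26% to 35% at 24 months) or if disclosure comes only later in the course. These figures describe opportunity for unblinding, not its occurrence. The bias in PART-O cannot be computed from the protocol.

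The point does not extend to contaminated treatment: patients who have finished their 4 weeks cannot be affected by later training of their therapist. No sample size figure changes. This is a minor point, worth making because the remedy is cheap.

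**What to change.** State one time in Sections 8.2 (both bullets), 10.1 and 16.1: control therapists are offered MI training, with the $200, only after the last 6-month PART-O interview at their site. This fits the protocol's own later wording and replaces undefined terms with an observable event.

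The change is to wording only. The cost falls on control therapists, who would wait about 6 months longer than under the earlier timing, or up to about 8 months at the longest discharge lag assumed above. Some may leave before being trained, and the offer may fall outside the roughly 1-year participation expected in Section 8.5. The possible exposure from the MI arm's initial training needs separate attention.
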